Taken together these findings suggest that relaxation music played on singing bowls may be beneficial in improving mood, decreasing stress, and improving sleep. Extending the previous work by co-PI [name] [19], this study seeks to compare the effects of listening to quartz crystal singing bowl music with guided relaxation on mood, stress and sleep in a larger sample of young adults. Participants will be randomly assigned to either the singing bowl (SB) or guided progressive muscle relaxation (PMR) condition. Participants will be asked to listen to singing bowl music or complete the PMR exercises for 10 minutes three time a week for four weeks (delivered online via the Qualtrics platform) and will then be given free access to the music or guided meditation for another four weeks whilst their use is monitored. Ratings of mood, stress and sleep will be completed at baseline, 4 weeks and 8 weeks. For one session per week, participants will be asked to complete visual analogue rating scales of their mood/stress immediately before and after the session to determine the acute effects of the intervention.

3. Study Design and Method

a) Hypothesis

Listening to singing bowl music will result in equivalent improvements in mood, stress and sleep compared with guided relaxation immediately after the session, and at 4- and 8-weeks post-intervention.

b) Design

Randomised controlled trial.

c) Intervention

Singing bowl music (SB)

The singing bowl relaxation music ('Tranquility' available on Spotify) was played by [name] and professionally recorded. The sound is produced by tapping the bowls and rubbing them with a rubber mallet. Each session took approximately 10 minutes.

Guided relaxation (PMR)

A guided progressive muscle relaxation audio (recorded by the NZ Cancer Society <https://www.youtube.com/watch?v=Zydrp3rfJdY>) and similar to the PMR script from the Anxiety and Phobia Workbook by Edmund Bourne [20]) was used. The session took approximately 12 minutes. Participants were instructed to start by sitting or lying comfortably, taking some deep breaths and then tense and relax muscles in a sequential manner from the head to the feet (see Appendix 6 for an example of the PMR script).

d) Outcome measures

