Profile of Mood States Abbreviated [21]. Participants are presented with a list of 40 words that describe feelings people have. They are asked to circle the number that best describes how they feel right now from 0 (not at all), 1 (a little), 2 (moderately), 3 (quite a lot) to 4 (extremely). Alogue scales - . A Total Mood Disturbance score (TMD) is also calculated by summing the totals for the negative subscales (Tension, Depression, Anger, Fatigue, Confusion), and subtracting the totals for the positive scales (Vigour, Esteem-related Affect [Note that 2 item are reverse scored for the ERA subscale]). See Appendix 3. The primary outcome measure is the TMD, but we will conduct secondary analyses to examine the effects of the interventions on the subscale scores.

Modified Auckland Sleep Questionnaire [22]. The Auckland Sleep questionnaire was developed to diagnose common sleep disorders in primary care. We will use the items about current sleep and asked participants to rate them in reference to the previous week (rather than the previous month as in the original questionnaire). The overall sleep quality rating will be used in the analysis (Appendix 4).

Visual Analogue Scales

To assess the acute effects of the intervention, participants will be asked to complete ratings of overall mood, relaxation, and stress before and after one session each week. Participants are asked to rate how they are feeling *right now* using a visual analogue scale (VAS) from 0 (worst I've ever felt not relaxed, not stressed,) to 100 (very stressed, very relaxed, best I've ever felt)[23, 24] see Appendix 5.

e) Objectives

Primary Objective

To determine if the effects of listening to singing bowl music are equivalent to that of progressive guided muscle relaxation on self-report measures of mood in young adults (Total Mood Disturbance of the POMS) at 4- and 8- weeks post intervention.

Secondary Objectives

To compare the effects of the interventions on:

- Profile of Mood States-Abbreviated (POMS) subscale scores
- Overall sleep quality from the Auckland Sleep Questionnaire
- VAS ratings of mood, stress and relaxation

Exploratory analyses will be undertaken to determine i) how frequently the participants use the interventions in weeks 4-8, and ii) the acceptability of the interventions.

4. Study population

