Participants will then be randomised to either the singing bowl (SB) (Tranquility by [name]) or the guided relaxation group (PMR; example script is in Appendix 6) and given access to the relevant audio on the qualtrics platform (to allow us to monitor when and for how long participants engaged with the intervention). Participants will be asked to listen to the relevant intervention 3 times a week for four weeks (each session is approximately 10 minutes). Before and after one session each week, participants will be asked to complete the visual analogue ratings scales to assess the acute effects of the intervention on their mood, stress and relaxation (Appendix 5). Participants will be sent reminders 3 x per week to complete the intervention.

Participants will be asked to complete the mood and sleep measures again after 4- (T2) and 8-weeks (T3)

The students will actively monitor participant's engagement in the study and send email reminders to complete the intervention sessions (Qualtrics is set up to automatically send email notifications to the study email address when participants complete each session so we can keep track of where they are up to) and the questionnaires at 4 and 8 weeks after the start of the study. After the first four weeks, participants will have free access to either the SB or PMR audio to use as much as they like, and we will monitor the frequency of use via the qualtrics app for the next four weeks. We will send out the link to the intervention weekly in weeks 4-8.

After completion of the 8 week questionnaire (T3) participants will be provided unlimited (and unmonitored) access to both audio tracks and will be asked to provide any feedback on the study.

6. Statistical Analysis

Primary outcomes

Difference scores between baseline (T1) and T2 (4 weeks), and T3 (8 weeks) for the POMS TMD will be calculated.

Secondary outcomes

- a) Difference scores between baseline (T1) and T2 (4 weeks), and T3 (8 weeks) for the POMS subscale scores and Auckland Sleep questionnaire will be calculated.
- b) The number of intervention sessions completed between T1 and T2, and T2 and T3.
- c) Feedback on the acceptability and effectiveness of each intervention.

Sample size

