A previous study examining the effects of an in person Tibetan singing bowl (n=62) session showed mean reductions of 0.49 to 1.23 (SD 0.19-1.05) in five POMS subscale scores [16]. A study with a much smaller group of teenage males (n= 11) showed significant reductions in POMS depression scores post-intervention [19]. In person PMR or Autogenic relaxation sessions in young soccer players (n=8) produced significant reductions in four of the six POMS-A subscales (mean difference 2.13 to 4.25; SD 2.38 to 4.47) [25]. As the current study is online rather than in-person, and the sessions are shorter, the effects may be somewhat smaller. Given this we are aiming to recruit a minimum of 100 participants (50 per group). This will provide > 90% power (2-sided $\alpha=0.05$) to detect a medium size effect of the intervention on the POMS subscales.

Analysis Plan

Univariate repeated measures ANOVA will be used to examine the effects of the intervention on the overall TMD score from the POMS, VAS scores and sleep scores. Repeated measures MANOVA will be used to examine changes in the POMS subscale scores.

Participants will be excluded from the analyses if they have not completed at least one intervention session per week for the first four weeks. The number of sessions completed during the first four weeks may be included as a covariate in the analyses.

7. Safety Concerns

Participants will be encouraged to contact us if they have any concerns. We will discuss the issue with the clinical advisor (with the participants consent) and encourage the participants seek support from their GP in the first instance. We will also have a list of support organisations available for participants.

8. Publication

All listed investigators will be co-authors on any presentation or manuscript published from this study. The principal investigators will be the first authors on the study manuscript.

9. References

1. Health Mo. Annual Data Explorer 2022/23: New Zealand Health Survey [Data File]. 2023.

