15	Uneasy	0	1	2	3	4
16	Restless	0	1	2	3	4
17	Unable to concentrate	0	1	2	3	4
18	Fatigued	0	1	2	3	4
19	Competent	0	1	2	3	4
20	Annoyed	0	1	2	3	4
21	Discouraged	0	1	2	3	4
22	Resentful	0	1	2	3	4
23	Nervous	0	1	2	3	4
24	Miserable	0	1	2	3	4
25	Confident	0	1	2	3	4
26	Bitter	0	1	2	3	4
27	Exhausted	0	1	2	3	4
28	Anxious	0	1	2	3	4
29	Helpless	0	1	2	3	4
30	Weary	0	1	2	3	4
31	Satisfied	0	1	2	3	4
32	Bewildered	0	1	2	3	4
33	Furious	0	1	2	3	4
34	Full of pep	0	1	2	3	4
35	Worthless	0	1	2	3	4
36	Forgetful	0	1	2	3	4
37	Vigorous	0	1	2	3	4
38	Uncertain about things	0	1	2	3	4
39	Bushed	0	1	2	3	4
40	Embarrassed	0	1	2	3	4

Appendix 4

Auckland Sleep questionnaire (current sleep)

Please answer the following:

a. Do you have problems getting to sleep, staying asleep, poor quality sleep, or waking early such that it affects your functioning the next day – this includes feeling excessively sleepy the next day?

No Yes

b. Does this occur 3 or more times per week?

No Yes

c. Has it been like this for more than one week?

No Yes

d. How long have you had this problem? _____

e. If **yes**, was there some event that caused this? (Please describe.)

Were there specific reasons for your poor sleep? i.e. baby crying, sick family member, partying too late, work/school requirements? _____

f. Do you need medication to help your sleep, mood or stress?

Please tick one:

Not during the past month

Less than once a week

Once or twice a week

Three or more times a week

g. If **yes**, what is the name of this medicine(s) _____

h. During the past week, how would you rate your sleep quality overall?

Please tick one:

Very good

Fairly good

Fairly bad

Very bad

Last time point only

Do you have any feedback on the intervention? What did you think about it? Did you like it?

Would you recommend the intervention you experienced to other rangitahi?

Thank you for answering the questions. You've now completed the study. Over the next few days you will receive an email with links to the progressive muscle relaxation and singing bowls tracks so you can use them whenever you like

Appendix 5

Visual analogue scales

Overall, how do you feel right now? Move the slider along the line to indicate your response.

0 = Worst I have ever felt 100 = Best I have ever felt

0 10 20 30 40 50 60 70 80 90 100

Q1.3 How relaxed do you feel right now? Move the slider along the line to indicate your response.

0 = Not relaxed 100 = Very relaxed

0 10 20 30 40 50 60 70 80 90 100

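### Sleep is one four-category rating analysed as a change from T1 without adjusting for T1, which gives away power and can hide a difference in the share with good sleep

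*Combined protocol and SAP*

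**What the plan says.** Section 3d names the sleep variable: "The overall sleep quality rating will be used in the analysis". Appendix 4, item h, shows that this is one question, "During the past week, how would you rate your sleep quality overall", with four ordered answers: Very good, Fairly good, Fairly bad, Very bad. No numeric codes are given.

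Section 6, Secondary outcomes, says that differences from T1 to T2 and T3 "for the POMS subscale scores and Auckland Sleep questionnaire will be calculated". The Analysis Plan then uses univariate repeated measures ANOVA to "examine the effects of the intervention on the overall TMD score from the POMS, VAS scores and sleep scores". The only covariate mentioned is the number of sessions completed, which may be included. The T1 rating is not a covariate.

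Section 3a expects "equivalent improvements in mood, stress and sleep compared with guided relaxation", and section 3e lists overall sleep quality as a secondary objective. No equivalence margin is stated for sleep or for any other outcome. The Sample size section gives 50 per group and a power figure for the POMS subscales only, so there is none for sleep.

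**The concern.** Subtracting one answer from another requires codes, and a four-point code is coarse and bounded. Someone who starts at Very good cannot improve and contributes at best a zero change. The difference score also carries the full noise of the T1 rating into the comparison. The plan does not say whether the ANOVA is run on the ratings or on the differences, but the arm-by-time test compares mean code changes either way.

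Two things are at stake. The sleep comparison may have less power than the same data could give. And a mean of codes may look the same in both arms when the arms differ in something readers care about, namely how many people sleep well. Both push towards finding no difference, which is the result the hypothesis favours.

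**Working it through.** **Inputs.** From the documents: four ordered categories (Appendix 4), difference scores and ANOVA without T1 adjustment (section 6), 50 per arm and two-sided 5% (Sample size). Assumed, because the documents give nothing: the T1 category split, the T1–T2 correlation ρ and the size of the arm effect. There is no stated power for sleep to reproduce.

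**Step 1. Why subtraction costs power.** For a continuous score with SD 1 at both visits, the residual variance is 2(1 − ρ) for a change score and 1 − ρ² after baseline adjustment. The ratio of adjusted to change-score variance is (1 + ρ)/2, which is 0.65, 0.75 and 0.85 at ρ = 0.3, 0.5 and 0.7. For a shift of 0.5 SD and 50 per arm, power ≈ Φ(0.5/√(2v/50) − 1.96), where v is the residual variance. At ρ = 0.5:

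- change score: v = 1, SE = 0.20, Φ(2.50 − 1.96) = 71%
- baseline-adjusted: v = 0.75, SE = 0.173, Φ(2.89 − 1.96) = 82%

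**Step 2. The four-category rating.** An underlying normal sleep score was simulated, cut at 15/55/25/5%, and shifted by 0.5 SD in one arm.

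| ρ | Difference of codes | Adjusted for T1 | Gain (points) |
|---|---|---|---|
| 0.3 | 44% | 65% | 21 |
| 0.5 | 53% | 69% | 16 |
| 0.7 | 67% | 79% | 12 |

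Independent runs agreed within 3 points. Type I error was near 5% for both methods.

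**Step 3. Other splits.** With splits of 15/50/28/7, 25/25/25/25 and 30/55/12/3 and the same correlations, the difference of equally spaced codes had 38–69% power. The full three-visit repeated measures ANOVA on codes had 38–73%. A linear model on the same codes adjusted for T1 had 60–82%, and a T1-adjusted proportional-odds model 62–83%. The two adjusted models were within 3 points of each other, so the gain comes from the adjustment and not from the ordinal form.

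**Step 4. What a mean of codes can hide.** This is a constructed example. Both arms start at 8/27/12/3 (Very good to Very bad). In the singing bowl arm 10 people move from Fairly bad to Fairly good, giving 8/37/2/3. In the PMR arm 10 move from Fairly good to Very good, giving 18/17/12/3.

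- Codes 0, 1, 2, 3: mean improvement is 10 × 1/50 = 0.20 in both arms, a contrast of exactly 0.
- Codes 0, 0.5, 1.5, 3: singing bowl 10 × 1/50 = 0.20, PMR 10 × 0.5/50 = 0.10.
- Codes 0, 1.5, 2.5, 3: singing bowl 10 × 1/50 = 0.20, PMR 10 × 1.5/50 = 0.30. The favoured arm reverses.
- Good sleep (Very good or Fairly good): 45/50 = 90% against 35/50 = 70%. The difference is 20 points, SE √(0.9 × 0.1/50 + 0.7 × 0.3/50) = 0.077, 95% CI 5 to 35 points.
- Proportional-odds model with arm only: odds ratio 0.91, 95% CI 0.43 to 1.95, p = 0.82.

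The opposite shifts at different cut-points cancel in a single odds ratio as they do in a mean. Only the proportion shows the difference.

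**The case against.** The strongest reply is that equal-interval scoring of a short ordered item is common and transparent, that the false-positive rate is sound (4.3–5.4% under every coding tried), and that sleep is a secondary outcome with no power claim attached. All of that stands. It also stands that the category split, correlation and effect are assumed, so no single power figure is a property of this plan, and that the pattern in step 4 was constructed and may not occur.

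A reader might infer that ANOVA on category codes is the fault and that an ordinal model is the cure. The working does not support this. A linear model on the same codes recovers nearly all the lost power once T1 is included, and the proportional-odds model misses the step 4 difference as well. The general point about subtracting versus adjusting for baseline also applies to other difference scores in section 6.

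A reader might also infer that better sleep coding would allow the equivalence in section 3a to be shown. It would not: with no margin stated, no coding or model can show it.

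The reply does not remove the fact that the adjusted analysis had higher power in every setting tried, uses data already collected, and costs almost nothing.

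**Conclusion.** The point holds as a free improvement for a secondary outcome. The planned sleep analysis is valid but inefficient. Under the 15/55/25/5% split and a 0.5 SD underlying shift, subtracting T1 gives about 44–67% power and adjusting for it 65–79%, a gain of 12 to 21 points. The size depends on those assumptions; the direction was the same across all splits and correlations tried. The figures take 50 analysed per arm. The exclusion of participants with too few sessions could lower that number, and the power of both methods with it.

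Separately, a mean of codes can be identical in both arms while the share with good sleep differs, so the sleep result needs a summary that readers can interpret directly. The documents do not support the stronger conclusions that the ANOVA is invalid or that an ordinal model is required.

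**What to change.** In section 6:

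- Replace the sleep difference score and ANOVA with a model of the T2 and T3 ratings containing arm, time, arm by time and T1 rating. Allow for repeated ratings on the same person by a random intercept, GEE or clustered standard errors.
- Choose in advance either a linear model on stated codes or a cumulative-logit model. Either is acceptable.
- At T2 and T3, report the category distribution by arm and the between-arm difference, with 95% CI, in the proportion rating sleep Very good or Fairly good. Keep this whichever model is chosen, since neither replaces it.
- State that a non-significant sleep result will not be described as equivalent, because no sleep margin is given.

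The cost is a few sentences of SAP text and slightly more analysis work. No new data are needed: the rating is already collected at T1, T2 and T3.

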
Appendix 1

Eligibility Questionnaire

The next few questions are to confirm that you are eligible to participate in the study. After that we will ask you to provide some information about you, and answer some questions about your mood and your sleep. You can then complete the first relaxation exercise, so make sure you are somewhere comfortable and quiet and have some headphones.

How old are you?

16 (16) ... 25 (25)

Do you have access to a mobile/tablet or laptop, and headphones so that you can access the intervention?

No (1) Yes (2)

Do you use singing bowls music regularly (more than once a month)?

No (1) Yes (2)

Do you use guided meditation regularly (more than once a month)?

No (1) Yes (2)

Are you currently receiving treatment from a psychologist or psychiatrist?

No (1) Yes (2)

Appendix 2

Demographic questionnaire

Now we want to know a little bit about you... What gender do you most identify as?

Male (1)

Female (2)

Non-binary/third gender (3)

Prefer to self-describe: (4) _____

Prefer not to say (5)

Q4.3 What is your ethnicity? (Select all those that apply)

New Zealand European (1)

Maori (2)

Samoan (3)

Cook Island Maori (4)

Tongan (5)

Niuean (6)

Chinese (7)

Indian (8)

Other, such as Dutch, Japanese, Tokelauan (9)

Q4.4 What is your first language?

Q4.5 Please tell us a bit about your education

Still at secondary school (1)

Completed secondary school (2)

At University/Tec (3)

Completed University/Tec (4)

Q4.6 What qualifications have you completed? (tick all that apply)

Nil (1)

NCEA Level 1 or equivalent (2)

NCEA Level 2 or equivalent (3)

NCEA Level 3 or equivalent (4)

Trade - Specify (5) _____

Professional - Specify (6) _____

Tertiary - Specify (7) _____

Other - Specify (8) _____

Appendix 3

Abbreviated POMS (Revised Version)

Below is a list of words that describe feelings people have. Please **CIRCLE THE NUMBER THAT BEST DESCRIBES HOW YOU FEEL RIGHT NOW.**

		Not At All	A Little	Moderately	Quite a lot	Extremely
1	Tense	0	1	2	3	4
2	Angry	0	1	2	3	4
3	Worn Out	0	1	2	3	4
4	Unhappy	0	1	2	3	4
5	Proud	0	1	2	3	4
6	Lively	0	1	2	3	4
7	Confused	0	1	2	3	4
8	Sad	0	1	2	3	4
9	Active	0	1	2	3	4
10	On-edge	0	1	2	3	4
11	Grouchy	0	1	2	3	4
12	Ashamed	0	1	2	3	4
13	Energetic	0	1	2	3	4
14	Hopeless	0	1	2	3	4

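### The primary TMD comparison is planned only in participants who used the audio in every one of weeks 1-4; an as-randomised analysis should be added, and sessions completed should not be a covariate

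*Combined protocol and SAP*

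**What the plan says.** Section 5 (Study Procedures) places randomisation after the baseline (T1) questionnaires and before use of the audio. The schedule is: "Participants will be asked to listen to the relevant intervention 3 times a week for four weeks". Staff monitor use and send reminders for the sessions and for "the questionnaires at 4 and 8 weeks after the start of the study"; neither questionnaire is restricted to people who kept up their sessions.

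The primary objective (section 3e) is one of equivalence on TMD: "To determine if the effects of listening to singing bowl music are equivalent to that of progressive guided muscle relaxation". The method in section 6 is: "Univariate repeated measures ANOVA will be used to examine the effects of the intervention on the overall TMD score from the POMS".

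Two sentences at the end of the Analysis Plan then govern who and what enters the models. The first is the exclusion: "Participants will be excluded from the analyses if they have not completed at least one intervention session per week for the first four weeks". The second is an option: "The number of sessions completed during the first four weeks may be included as a covariate in the analyses". The same quantity is secondary outcome b): "The number of intervention sessions completed between T1 and T2, and T2 and T3".

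The exclusion is not limited to any one analysis, so it covers the TMD ANOVA. Section 6 names no as-randomised set, no sensitivity analysis and no method for missing data.

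**The concern.** Whether someone completes a session in each of four weeks is behaviour that follows allocation and may be influenced by it. The two tasks are not alike: section 3c describes about 10 minutes of listening in one arm and about 12 minutes of active muscle work in the other. If one arm loses more people under the rule, or loses people whose mood is moving differently, the groups left are no longer those that randomisation made comparable. The estimated TMD difference could then be moved towards or away from zero. In an equivalence trial either error matters, since a false difference and a hidden one both change the answer.

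The optional covariate raises a related problem. Adjusting for a variable measured after randomisation can remove or distort part of the arm effect, and leaving its use open allows the choice to be made once the data are known.

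**Working it through.** **What the documents supply.** 50 participants per group (section 6, Sample size) and 3 sessions x 4 weeks = 12 sessions (section 5). They give no expected adherence, exclusion rate, adherence-mood correlation or SD of TMD change. There is thus no figure of the plan's own to reproduce on this point, and every other input below is an assumption.

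**1. Size of bias from unequal retention.** Suppose no true arm difference, a correlation r between adherence and mood change, and retention of the most adherent fraction k in each arm. The mean change among those retained is r x phi(z)/k, with z = Phi^-1(1 - k). The bias, in SD of TMD change, is

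r x [phi(z_b)/k_b - phi(z_a)/k_a].

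phi(z)/k is 0.195, 0.274, 0.350 and 0.497 for k = 0.90, 0.85, 0.80 and 0.70. The standard error is sqrt(1/(50 k_a) + 1/(50 k_b)). Type I error is for a two-sided 5% test of a difference, by normal approximation.

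| Retention | Bias, r = 0.3 / 0.5 | SE | Bias/SE | Type I error |
|---|---|---|---|---|
| 80% v 80% | 0 / 0 | 0.224 | 0 | 5% |
| 90% v 80% | 0.046 / 0.077 | 0.217 | 0.21 / 0.36 | 5.5% / 6.5% |
| 85% v 70% | 0.067 / 0.111 | 0.228 | 0.29 / 0.49 | 6.0% / 7.8% |
| 90% v 70% | 0.09 / 0.15 | 0.225 | 0.40 / 0.67 | 6.9% / 10.2% |

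**2. How many the rule might exclude.** If each session is completed independently with probability p, a week contains at least one session with probability 1 - (1 - p)^3, and the rule keeps [1 - (1 - p)^3]^4.

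- p = 0.6: 0.936^4 = 77%
- p = 0.7: 0.973^4 = 90%
- p = 0.8: 0.992^4 = 97%
- p = 0.9: 0.999^4 = 99.6%

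Retention is lower if missed sessions cluster within weeks. Week 1 may seldom trigger exclusion, because the introduction to the Appendix 1 questionnaire tells participants, of the time just after the baseline questions: "You can then complete the first relaxation exercise".

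**3. The covariate, if it is used.** Assume sessions differ between arms by 0.2 or 0.5 SD among all randomised, with the same cut-off in both arms. With 80% retained in the higher-use arm, the gap left in the retained set is 0.111 or 0.256 SD; with 90%, 0.137 or 0.320 SD. Multiplying by r = 0.3-0.5 gives a shift in the adjusted difference from 0.111 x 0.3 = 0.03 to 0.320 x 0.5 = 0.16 SD.

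**4. What an as-randomised analysis would recover.** If a fraction f of those excluded still give T2, independently of their mood, the observed mean becomes r x phi(z)(1 - f)/(k + f(1 - k)). At 85% v 70% and f = 0.5, the bias falls from 0.067-0.111 to 0.024-0.039 SD. At f = 1 it is 0; at f = 0 nothing is gained from the observed data.

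**The case against.** The best defence is that the rule is mild and the setting favourable. It asks for one of three requested sessions a week. Both arms share the schedule, the three weekly reminders and the active monitoring, and psychology-pool participants receive course credit. Exclusions may then be few and similar, in which case there is little or no bias. An adherer set is also a proper analysis for an equivalence objective. All of this stands, and it limits the severity. It does not supply the missing analysis: the plan still has no comparison of the arms as randomised.

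Three stronger readings are tempting, and the documents do not support them.

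- A reader might infer that the rule is unrelated to the amount of use, since 3+3+3+0 (9 sessions) is dropped and 1+1+1+1 (4 sessions) is kept. Those are extremes. Counting all weekly patterns of 0-3 sessions equally, the share kept rises steadily from 3% at a total of 4 to 80% at 9, and is 100% from 10 upwards.
- A reader might infer that unequal adherence would go unseen. Use of the audio is recorded and sessions between T1 and T2 are a listed outcome. The gap is narrower: the plan does not commit to reporting exclusions by arm.
- A reader might expect heavy losses because one empty week is enough. If each week has an independent 5% or 10% chance of being empty, 1 - 0.95^4 = 19% or 1 - 0.90^4 = 34% are excluded. With independent sessions, however, that corresponds to only about 63% or 54% of sessions completed. Completion of 70-90% would exclude only about 10% to 0.4%.

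The covariate is optional, so its figures apply only if it is used and the arms differ in use.

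**Conclusion.** The concern holds as a gap in the analysis plan. The sole analysis set for the primary TMD comparison is defined by behaviour after randomisation, and a post-randomisation outcome may be added as a covariate. Bias requires that retention, or the relation of adherence to mood, differs by arm; its direction cannot be told from the documents. In the milder assumed scenarios it is 0.05-0.11 SD, below half a standard error, with type I error of about 5.5-7.8%. At 90% v 70% retention it is 0.09-0.15 SD, up to about two thirds of a standard error, with type I error of about 7-10%.

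It would go too far to conclude that the trial's result will be biased, or badly so: nothing in the documents establishes unequal retention or its size. The rating is moderate (should fix), and it rests on the missing as-randomised analysis.

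**What to change.** 1. Make the primary TMD analysis all randomised participants in their assigned arm, regardless of sessions completed, using all available T1-T3 data. State the missing-data assumption; a mixed model with arm, time and their interaction, valid if data are missing at random, is one option. State also that T2 and T3 are sought from everyone randomised, including those who stop using the audio.
2. Keep the present rule as a named per-protocol set, reported alongside. A requirement that both sets support equivalence can be added only once the plan sets a margin, and it would make the claim harder to meet.
3. Remove sessions completed as a covariate from the efficacy models and report it by arm as the outcome it already is.
4. Report the number excluded under the rule by arm.

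The repeated measures MANOVA for the subscales can stay. The cost is revised wording, one extra analysis and, if chosen, a change of model for TMD; the T2 and T3 questionnaires and reminders are already planned. The limit is follow-up: if people who stop their sessions also skip T2 and T3, the as-randomised result leans on the missing-data assumption and gains little.
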